## 4.2 Response Criteria and Statistical Considerations

4.2.1 This is a phase II study of continuous hyperthermia peritoneal perfusion (HIPEC) in patients with desmoplastic round cell tumor (DSRCT) and non-DSRCT patients. The primary objective is to assess the efficacy of this treatment, with a primary endpoint of time to relapse. The historical median time to relapse for DSRCT patients without HIPEC treatment was about 1.6 months. A maximum of 22 patients will be enrolled in MDACC at an estimated accrual rate of 1 patient every 2 months including a total of 5 non-DSRCT patients. Patients will be followed up until relapse, death or for 6 months after the treatment, whichever ever occur first. It would be encouraging if the median time to relapse could increase to 3.2 months with the HIPEC treatment. The toxicity and efficacy will be monitored during the study, and all the data will be used to update the prior distributions for toxicity and efficacy parameters. The study will be stopped for toxicity and futility based on the following stopping rules.

4.2.2 The primary endpoint TTP will be monitored using the method of Thall et al. (23). Denote median (TTP) =  $m_H$  for patients without HIPEC treatment and  $m_E$  for patients with HIPEC treatment. We assume that TTP is distributed exponentially with mean of  $m_H$  and  $m_E$ , respectively, in patients without and with HIPEC treatment. Under a Bayesian model, we will further assume that  $m_H$  has an inverse gamma (IG) prior with parameters (16.2, 24.3), with a mean of median TTP=1.6 months and variance = 0.18. We also assume that  $m_E$  follows IG prior (2.03, 1.64) with the same median TTP as  $m_H$  but with a much larger variance (100) to reflect much greater uncertainty about TTP in patients with HIPEC treatment. The TTP data will be monitored continuously, and the study will be terminated early if  $\Pr(m_H + d < m_E \mid \text{data}) < 0.05$ , where  $d = 1.6$  month. Specifically, the trial will be stopped early if, given the current data, there is less than 5% chance that the median TTP will improve by more than 1.6 month in patients treated with HIPEC, compared to those without HIPEC treatment. The operating characteristics of this decision rule are summarized in [Table 1](#).

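### The futility rule in 4.2.2 has no minimum number of patients and starts close to its cutoff, so one relapse dated before about 1.0 to 1.4 months would stop the trial

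*Combined protocol and SAP*

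**What the plan says.** Section 4.2.1 gives the benchmark, "The historical median time to relapse for DSRCT patients without HIPEC treatment was about 1.6 months", and the target, "It would be encouraging if the median time to relapse could increase to 3.2 months". For m_H, section 4.2.2 specifies an inverse gamma (IG) distribution, written as a "prior with parameters (16.2, 24.3), with a mean of median TTP=1.6 months and variance = 0.18". The parameter for HIPEC patients, m_E, is said to be one that "follows IG prior (2.03, 1.64) with the same median TTP as" its historical counterpart. The spread is deliberately made wider; in the plan's terms, "but with a much larger variance (100) to reflect much greater uncertainty about TTP in patients with HIPEC treatment".

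The stopping rule is Pr(m_H + 1.6 < m_E | data) < 0.05, explained as stopping when "there is less than 5% chance that the median TTP will improve by more than 1.6 month in patients treated with HIPEC". Looks are continuous: "The TTP data will be monitored continuously, and the study will be terminated early if" that condition is met. No minimum number of patients, events or months of follow-up is given.

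Table 1 reports early-stop probabilities of 0.998, 0.775, 0.178 and 0.126 at true medians of 1, 1.6, 3.2 and 4 months. In the 1-month row the 25th percentile of patients treated is 1.

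Two other sections bear on when a relapse can be recorded. Section 4.5.5 schedules CT or MRI at 3 and 6 months only (within 2 weeks), with a physical examination at one month. Section 4.8.1 defines progression radiographically.

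**The concern.** A rule with no minimum can act on one patient. Whether it does depends on how far the prior sits from the cutoff. Here the m_E prior is meant to express uncertainty, but most of its mass lies below the historical median, so little evidence is needed to cross 0.05. With at most 22 patients and a rare tumour, a treatment that meets the protocol's own target could be abandoned on one or two early outcomes. Table 1, on which the rule would be judged acceptable, may understate that chance.

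**Working it through.** **Inputs (4.2.1, 4.2.2, Table 1).** m_H ~ IG(16.2, 24.3); m_E ~ IG(2.03, 1.64); d = 1.6 months; cutoff 0.05; one patient every 2 months; follow-up 6 months. *Assumptions:* 20 patients, because the Table 1 percentiles top out at 20 (the text gives 22, including 5 non-DSRCT), and a look at each event. Section 4.2.2 defines m as a median and then says "We assume that TTP is distributed exponentially with mean of" m_H and m_E, so both readings are run. The truth is always a median, as Table 1 labels it.

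**1. Priors.** For IG(a, b) the mean is b/(a−1) and the variance b²/[(a−1)²(a−2)].
- m_H: mean 24.3/15.2 = 1.60; variance 24.3²/(15.2² × 14.2) = 0.18; median 1.53. The stated mean and variance are reproduced.
- m_E: mean 1.64/1.03 = 1.59; variance 1.64²/(1.03² × 0.03) = 84.5, which is consistent with the stated 100 before the parameters were rounded; median 0.96. About 73% of the mass lies below 1.6 months.
- Before any data, Pr(m_E > m_H) = 0.29 and Pr(m_E > m_H + 1.6) = 0.093.

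**2. One relapse.** With k events and total follow-up T, m_E updates to IG(2.03 + k, 1.64 + cT), where c = 1 (m as mean) or ln 2 (m as median). Integrating over the m_H prior for one patient relapsing at time t:

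| t (months) | m as mean | m as median |
|---|---|---|
| 0.5 | 0.031 | 0.026 |
| 1 | 0.052 | 0.038 |
| 2 | 0.109 | 0.072 |
| 2.5 | 0.143 | 0.092 |
| 3 | 0.181 | 0.114 |

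The 0.05 boundary falls at t = 0.96 month (mean) or 1.38 months (median). At a true median of 3.2 months the chance that the first patient relapses by then is 1 − 2^(−0.96/3.2) = 0.19 or 1 − 2^(−1.38/3.2) = 0.26. Both times precede the second patient's entry at 2-month spacing.

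**3. Whole trial, exact relapse dates (simulation).**

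| True median (months) | Table 1 | m as mean | m as median |
|---|---|---|---|
| 1 | 0.998 | 0.99 | 1.00 |
| 1.6 | 0.775 | 0.76 | 0.97 |
| 3.2 | 0.178 | 0.27–0.28 | 0.46–0.48 |
| 4 | 0.126 | 0.20–0.22 | 0.33 |

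Table 1 is not reproduced. The mean reading comes close at 1 and 1.6 months but not at 3.2 and 4. The nearest variant adds an unstated minimum of 2 patients (0.995, 0.744, 0.179, 0.135), which conflicts with the 25th percentile of 1 in the 1-month row. At 3.2 months, stops with at most 3 patients treated make up 0.249 of 0.275 (91%, mean) or 0.365 of 0.47 (78%, median).

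**4. With a minimum of 5 treated patients, exact dates.** At 3.2 months the stop probability falls to 0.06–0.09 (mean) or 0.26–0.31 (median), the range reflecting look conventions. At 1.6 months it goes from about 0.76 to 0.64–0.68 (mean) or from 0.97 to about 0.96 (median). Average patients at 1.6 months rise from 7.8 to about 12 (mean) or from 4.0 to 7.5 (median).

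**5. Relapses dated only at the 3- and 6-month scans, no minimum.** Stop probability at 3.2 months: 0.00 under both readings. At 1.6 months: 0.00 (mean), below 0.01 (median). At 1 month: 0.00 (mean), about 0.11 (median).

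**The case against.** The strongest reply is that the protocol does not schedule the data that this harm needs. Progression is radiographic and the first scheduled scan is at 3 months, or about 2.5 at the edge of the window. One relapse recorded at 2.5 months leaves the probability at 0.143 or 0.092, so it cannot stop the trial. This stands. A reader might infer that the trial as scheduled is likely to stop on its first relapse, and the documents do not support that. An early stop needs unscheduled imaging, a relapse called at the one-month examination, or an early death if deaths count as events, which 4.2 does not settle. But Table 1 cannot rest on scan-only dates, because 0.998 and 0.775 are out of reach under them, and a historical median of 1.6 months also implies relapses recorded before 3 months.

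Second, Table 1 already discloses early stopping, including after one patient. That is true, but its 0.178 is below what the first patient alone contributes. The lower percentile of 2 in its 3.2-month row is no evidence either way: with 17.8% stopping early, the 25th percentile should equal the maximum.

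Third, a contrast with toxicity monitoring, which begins at 8 patients, is tempting but overstated. Section 4.2.3 also stops earlier once 4 toxicities occur. The fair difference is 4 events against 1.

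Fourth, the prior need not be called wrong. Since m is itself a median time, the phrase about equal medians can be read as equal prior means, which holds. Re-centring the prior at a median of 1.53 would break the stated mean and variance, so no replacement is proposed.

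**Conclusion.** The point holds in conditional form. Section 4.2.2 sets no minimum, and the m_E prior leaves only 0.093 probability on the target gain before any data. If relapses are dated when they occur, one relapse before 0.96 or 1.38 months ends the trial. At the 3.2-month target the first patient alone does so with probability 0.19 or 0.26, and the rule as written stops with probability about 0.27 or 0.47, against 0.178 in Table 1.

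This rests on exponential times, 20 patients at one per 2 months, looks at each event, and events recorded before the 3-month scan. With scan-only dating the problem reverses: the rule almost never stops, even when there is no gain over history. Either way, Table 1 does not describe the rule together with the schedule.

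**What to change.** In 4.2.2:
- State a small minimum number of treated patients before the futility rule applies. Five is an example; other small values could be defended, and the choice should be made on the rerun operating characteristics.
- Say that the two priors share a mean, not a median.
- State how relapse is dated, whether relapses found off schedule and deaths count as events, and whether m is a mean or a median.
- Rerun Table 1 for the rule actually used, with the event-dating convention that the scan schedule will produce.

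The work is wording and one table. Under exact dating, a minimum of 5 costs about 3.5 to 4 more patients treated on average when there is no benefit. It also lowers the stop probability at 1.6 months from about 0.76 to 0.64–0.68 (m as mean) or from 0.97 to 0.96 (m as median). Under scan-only dating the minimum changes nothing at the 3.2-month target, and the rerun would instead show whether the rule can detect futility at all.

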### 1.0 Primary objectives of the study

**Primary objective 1:** To determine the efficacy of HIPEC using hyperthermic cisplatin given as a continuous perfusion after complete abdominal tumor excision in patients with DSRCT.

**Primary objective 2:** To determine the morbidity of extensive tumor resection and HIPEC on patients with DSRCT and other non-carcinoma tumors with extensive abdominal disease.

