4.2.3 In addition, toxicity will be monitored closely in all patients. The evaluation of the toxicity data will begin after enrollment of 8 patients. Denote the probability of toxicity by  $\theta_E$ , where toxicity is defined as any Grade 3 or greater renal, cardiac, respiratory or Grade 4 hematologic complications attributable to HIPEC. We assume  $\theta_E \sim \text{beta}(0.6, 1.4)$ . Our stopping rule is given by the following probability statement:  $\Pr(\theta_E > 0.30 \mid \text{data}) > 0.8$ . That is,

we will stop the trial if, at any time during the study, we determine that there is more than 80% chance that the toxicity rate is more than 30%. Stopping boundaries corresponding to this stopping rule are to terminate the trial if (# Grade 3 or greater renal, cardiac, respiratory or Grade 4 hematologic complications) / (# patients evaluated)  $\geq 4/8, 5/9, 6/12, 7/15, 8/18$ . That is, the trial will be stopped if 4 or more patients out of 8 patients, 5 or more patients out of 9 patients, and 6 or more patients out of 10, 11 and 12 patients, 7 or more patients out of 13, 14 and 15 patients, 8 or more patients out of 16, 17, 18 patients experience toxicity. Please note that for the first 8 patients, if 4 or more out of 4-7 patients experience toxicity, the trial will also be stopped, because the stopping boundary is already passed. The operating characteristics are summarized in [Table 2](#).

4.2.4 Analysis Plan: For discrete or categorical data, descriptive statistics will include tabulations of frequencies. For continuous data, summary statistics including n, mean, standard deviation, median, minimum and maximum will be computed. The median time to progression and its 95% confidence interval will be estimated. Kaplan-Meier method, Log rank test and Cox proportional hazards regression modeling will be utilized to analyze time to progression and overall survival. The study will use Department of Biostatistics Clinical Trial Conduct website to conduct/monitor with regard to the defined Bayesian rules.

Table 1. Operating characteristics for the design

True median Time to progression (month)	Pr(stop early)	Average Number of Patients Treated (25th, 75th percentiles)
1	0.998	4 (1,5)
1.6	0.775	9 (2,18)
3.2	0.178	17 (2,20)
4	0.126	18 (20,20)

Table 2.

True toxicity rate	Early Stopping Probability
0.1	0.006
0.2	0.094
0.3	0.344
0.4	0.665
0.5	0.897

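### Table 1 does not give the operating characteristics of the futility rule in section 4.2.2: one row is impossible, the simulated maximum is 20 rather than 22, and the stop rates do not follow from the rule as stated

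*Combined protocol and SAP*

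**What the plan says.** Section 4.2.1 gives the size of the trial: "A maximum of 22 patients will be enrolled in MDACC at an estimated accrual rate of 1 patient every 2 months". It describes that total as "including a total of 5 non-DSRCT patients". Each patient is followed for at most 6 months. The target is a median time to relapse of 3.2 months, set against this benchmark: "The historical median time to relapse for DSRCT patients without HIPEC treatment was about 1.6 months".

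Section 4.2.2 stops the trial if Pr(m_H + 1.6 < m_E | data) < 0.05, with inverse gamma priors IG(16.2, 24.3) for m_H and IG(2.03, 1.64) for m_E. It introduces m as the median and in the next sentence makes it the mean of the exponential. Monitoring is continuous, with no first look stated. It then says "The operating characteristics of this decision rule are summarized in" Table 1.

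The size column of Table 1 is headed "Average Number of Patients Treated (25th, 75th percentiles"). Its rows are:

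| True median (months) | Average N (quartiles) | Pr(stop early) |
|---|---|---|
| 1 | 4 (1, 5) | 0.998 |
| 1.6 | 9 (2, 18) | 0.775 |
| 3.2 | 17 (2, 20) | 0.178 |
| 4 | 18 (20, 20) | 0.126 |

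On who counts, section 4.2.1 says "all the data will be used to update the prior distributions for toxicity and efficacy parameters". Primary objective 1 in section 1.0 concerns HIPEC "given as a continuous perfusion after complete abdominal tumor excision in patients with DSRCT".

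**The concern.** A reader judging the futility rule has only Table 1 to go on. It offers a 17.8% chance of wrongly stopping a treatment that meets the target, and a 77.5% chance of stopping one no better than history. If the table was run for a different trial or under unstated settings, those error rates are not the ones the trial will have.

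Three features raise doubt. One row contradicts itself. No sample size above 20 appears, although 22 are planned. And the rule has no stated first look, so a single early relapse can end the trial, which sits badly with low stop rates at 3.2 and 4 months.

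**Working it through.** **Inputs.** Priors, margin of 1.6, cutoff of 0.05, exponential model and continuous monitoring are from section 4.2.2. Maximum N, accrual of one patient per 2 months and 6-month follow-up are from section 4.2.1. The priors are as described: IG(16.2, 24.3) has mean 24.3/15.2 = 1.60 and variance 0.18. IG(2.03, 1.64) has mean 1.64/1.03 = 1.59 and variance 84.5, against a stated 100, a gap that rounding of the parameters explains.

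**1. The 3.2-month row.** A 25th percentile of 2 needs at least 25% of trials to end with 2 or fewer patients. Only 17.8% stop early at all. The other 82.2% end at the maximum, so the 25th percentile must be the maximum.

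**2. The simulated maximum.** At 4 months 87.4% of trials run to the maximum and both quartiles are 20, so the maximum was 20. The averages agree. With stop probability p, the average lies between (1-p)Nmax + p and (1-p)Nmax + p(Nmax-1):

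| Nmax | 3.2 months (printed 17) | 4 months (printed 18) |
|---|---|---|
| 17 | 14.2-16.8 | 15.0-16.9 |
| 20 | 16.6-19.8 | 17.6-19.9 |
| 22 | 18.3-21.8 | 19.4-21.9 |

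Twenty-two cannot give 17 or 18, and 17 (DSRCT only) cannot give 18 or 20.

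**3. Table 2.** Section 4.2.3 stops the trial when "there is more than 80% chance that the toxicity rate is more than 30" percent. An exact binomial recursion with the beta(0.6, 1.4) prior, checked after each patient from 8 to Nmax-1, gives 0.007/0.094/0.345/0.669/0.895 for Nmax = 20 and 0.007/0.097/0.362/0.697/0.913 for Nmax = 22. Printed: 0.006/0.094/0.344/0.665/0.897.

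**4. Stopping at the first relapse.** After e relapses in T person-months, m_E | data ~ IG(2.03 + e, 1.64 + kT), with k = 1 if m is the mean and k = ln 2 if it is the median. For e = 1, solving Pr(m_H + 1.6 < m_E) = 0.05 gives kT = 0.959. The trial therefore stops if T is below 0.959 (mean) or 0.959/0.693 = 1.384 (median). Person-time to the first relapse is exponential whatever the accrual pattern, so Pr(stop at first relapse) = 1 - 2^(-T/median):

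- m as mean: 1 - 2^(-0.959/3.2) = 0.188 and 1 - 2^(-0.959/4) = 0.153.
- m as median: 1 - 2^(-1.384/3.2) = 0.259 and 1 - 2^(-1.384/4) = 0.213.

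All four exceed the printed whole-trial rates of 0.178 and 0.126.

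**5. Whole-trial stop rates.** Simulation with N = 17 or 22, 6-month censoring, exact relapse dates and looks from patient 1 (10,000 to 40,000 trials per cell):

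| Reading | 1.6 months | 3.2 months | 4 months |
|---|---|---|---|
| Printed | 0.775 | 0.178 | 0.126 |
| m as mean, continuous looks | 0.74-0.78 | 0.27-0.28 | 0.20-0.21 |
| m as median, continuous looks | 0.95-0.98 | 0.46-0.48 | 0.33-0.35 |
| m as mean, looks at enrolments, Poisson entry (lowest) | 0.717 | 0.235 | 0.171 |
| m as median, same (lowest) | 0.945 | 0.421 | 0.283 |

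The 1.6-month rate is reproduced with m as the mean. The 3.2- and 4-month rates are not reproduced on either scale.

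**6. Dating of relapses.** Section 4.8.1 defines progression radiographically, and section 4.5.5 scans only at 3 and 6 months, within 2 weeks either way. The plan does not say how a relapse between visits is dated. Pr(stop) at 1.6 / 3.2 months becomes:

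- First-month relapses found at the one-month examination and the rest at scans (an assumption): 0.61-0.69 / 0.19-0.23 with m as median, 0.17-0.20 / 0.04-0.05 with m as mean.
- Scans at exactly 3 and 6 months only: about 0.01 or less / 0.
- All scans two weeks early: 0.10-0.14 / at most 0.004 with m as median, and 0 with m as mean.

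The reason is simple. Each scan-dated relapse carries at least 2.5 person-months. With m as mean, the threshold at 22 relapses is 48.4 person-months against 22 x 2.5 = 55, and no smaller count has a higher threshold per relapse, so the rule cannot fire. With m as median it can first fire at 6 relapses (15.0 against 15.42), or at 15 if scans are at exactly 3 months (45 against 45.25).

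**The case against.** The strongest reply is that Table 1 may be a sound run of this rule under settings that were not written down. With a maximum of 20, m as the mean, looks at enrolments and a first look after patient 2, the stop rates at 3.2 and 4 months come to 0.17-0.18 and 0.11-0.12, close to print, and the 1.6-month rate to 0.71-0.72. Fixing m_H at 1.6 as well gives 0.994-0.996 / 0.757-0.775 / 0.191-0.193 / 0.117-0.127, with averages of 3.6-4.0 / 8.6-9.1 / 16.7-16.8 / 17.8-18.0. That is a near match, and it may be what was done. But the cap of 20 and the fixed m_H contradict sections 4.2.1 and 4.2.2, and the delayed first look appears nowhere in a rule described as continuous. The match is also incomplete: this run gives a 25th percentile of 2 where the 1-month row prints 1, and 20 where the 3.2-month row prints 2. The quartiles cut both ways, since starting at patient 1 with looks at enrolments gives 1 in the 1.6-month row where 2 is printed.

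Other limits stand. The (2, 20) cell is probably a slip for (20, 20). The choice of 20 or 22 moves Pr(stop) by only about 0.03 and mainly misstates the average N. Table 2 is corroboration only: a final look at patient 20 itself gives 0.362 and 0.697 at true rates of 0.3 and 0.4, the same as a cap of 22 with its last look at 21. Finally, the claim that the true false-stop rate is above 17.8% depends on exact dating. Across the dating conventions and both scales, the rate at 3.2 months runs from 0 to 0.48, so the direction of the error is not settled. That is itself a reason to state the convention.

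**Conclusion.** The concern holds and must be fixed. Two parts follow from the printed table alone: the 3.2-month row is impossible, and the simulated maximum was 20 rather than 22 or 17. The third follows from the printed priors: with continuous looks and exact dates, the first relapse alone gives stop probabilities (0.188 and 0.153) above the printed totals (0.178 and 0.126). Confidence in these is high.

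On that reading, a treatment that reaches the 3.2-month target is stopped in about 27-28% of trials with m as mean, or 46-48% with m as median. Confidence in these ranges is moderate, since they rest on exact relapse dates and looks from patient 1.

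Correcting the table changes no stopping decision by itself. The scale of m and the dating of relapses do. A first relapse at 1.2 person-months stops the trial with m as median (threshold 1.384) and not with m as mean (0.959), and under scan-only dating with m as mean the rule can never stop the trial.

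**What to change.** In section 4.2.2, state:

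- one scale for m, mean or median;
- the first look;
- whether the five non-DSRCT patients enter the rule, so that its maximum is 17 or 22;
- how a relapse between visits is dated.

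Then rerun the simulation with one patient per 2 months, 6-month follow-up and the actual assessment schedule with its 2-week window. Replace every entry of Table 1, percentiles included, and print the settings beneath it. If the existing run used other settings, state them and reconcile them with sections 4.2.1 and 4.2.2. Rerun Table 2 for the same maximum and state its last look.

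The cost is one simulation rerun, two replaced tables and a few sentences. The restated rates may look worse: more false stops at 3.2 and 4 months under exact dating, or little futility stopping at 1.6 months if relapses are dated at scans.

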4.4.2 Patients who progress will be offered other treatment alternatives

- 4.5 On study evaluation
  - 4.5.1 Patients will undergo laboratory tests, imaging and physical exam as per on study criteria.
  - 4.5.2 During HIPEC patients will have continuous core temperature monitoring by the esophageal probe and bladder probe. Peritoneal temperature is measured every 10-15 minutes by up to eight probes placed either beneath the peritoneal surface or at the influx and efflux catheters. If the temperatures are increasing above 40°C ( $\pm 1$ ), the temperature of the perfusate will be reduced. If the temperature readings are too low, the emphasis of the manual agitation will be redirected to that area of the abdomen.
  - 4.5.3 Patients will be followed postoperatively with daily CBC, sodium, potassium, chloride, carbon dioxide, BUN, creatinine, AST, ALT, calcium, albumin, magnesium, phosphorous, total bilirubin, alkaline phosphatase, amylase for 5 +/-2 days and then twice weekly until discharge; and post-discharge at day 14 +/-3 days and day 30 +/- 3 days and at 3 and 6 month (+/- 2 weeks) follow-up (Appendix 1) Adverse events will be assessed on the same timetable.
  - 4.5.4 Patients will be monitored in the PICU no less than 48 hours. If necessary, adult patients will be admitted to ICU.
  - 4.5.5 Evaluation of measurable disease will be performed one month, 3 months and 6 months postoperatively (+/- 2 weeks) using CT or MRI and physical exam. (CT or MRI scan performed only at 3 and 6 months)
  - 4.5.6 Audiology evaluation will also be performed at one month evaluation.
- 4.6 Concurrent Therapies
  - 4.6.1 Patients will be allowed to proceed with any post-operative chemotherapy including allogeneic or autologous bone marrow transplantation. No concurrent medications will be given at the time of study drug administration since this is only a 90 minute period in the operating room. However, baseline medications and all medications through the 30 days follow up will be entered into PDMS/CORe.
- 4.7 Pharmacokinetics (Optional)
  - 4.7.1 Blood and peritoneal fluid samples (2.0 ml) will be collected in purple top tubes, centrifuged, and supernatant or plasma collected and stored at -20°C until analyzed.
  - 4.7.2 Blood and peritoneal fluid will be collected prior to the start of cisplatin-HIPEC and then at times 0, 30, 60 and 90

minutes. An additional blood sample will be collected 24 hours (+/- 8 hours) after the start of HIPEC.

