#### 4.9 Serious Adverse Event Reporting (SAE)

An adverse event or suspected adverse reaction is considered “serious” if, in the view of either the investigator or the sponsor, it results in any of the following outcomes:

- Death
- A life-threatening adverse drug experience – any adverse experience that places the patient, in the view of the initial reporter, at immediate risk of death from the adverse experience as it occurred. It does not include an adverse experience that, had it occurred in a more severe form, might have caused death.
- Inpatient hospitalization or prolongation of existing hospitalization
- A persistent or significant incapacity or substantial disruption of the ability to conduct normal life functions.
- A congenital anomaly/birth defect.

Important medical events that may not result in death, be life threatening, or require hospitalization may be considered a serious adverse drug experience when, based upon appropriate medical judgment, they may jeopardize the patient or subject and may require medical or surgical intervention to prevent one of the outcomes listed in this definition. Examples of such medical events include allergic bronchospasm requiring intensive treatment in an emergency room or at home, blood dyscrasias or convulsions that do not result in inpatient hospitalization, or the development of drug dependency or drug abuse (21 CFR 312.32).

- **Important medical events as defined above may also be considered serious adverse events. Any important medical event can and should be reported as an SAE if deemed appropriate by the Principal Investigator or the IRB.**
- All events occurring during the conduct of a protocol and meeting the definition of a SAE must be reported to the IRB in accordance with the timeframes and procedures outlined in "University of Texas M. D. Anderson Cancer Center Institutional Review Board Policy on Reporting Serious Adverse Events". Unless stated otherwise in the protocol, all SAEs, expected or unexpected, must be reported to the IRB, regardless of attribution (within 5 working days of knowledge of the event).
- **All life-threatening or fatal events**, that are unexpected, and related to the study drug, must have a written report submitted within 24 hours (next working day) of knowledge of the event to the IRB.
- **The MDACC "Internal SAE Report Form for Prompt Reporting" will be used for reporting to the IRB.**

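### Three counted toxicities in the first 3, 4 or 5 patients are a stronger signal than the plan's own 4/8 stop, yet 4.2.3 attaches no action to them; a one-sentence enrolment hold would close this narrow gap

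*Combined protocol and SAP*

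**What the plan says.** Section 4.2.3 defines a counted toxicity as a renal, cardiac or respiratory event of grade 3 or worse, or a grade 4 haematological event, attributed to HIPEC. The prior on the rate is beta(0.6, 1.4). The rule is general in time: "we will stop the trial if, at any time during the study, we determine that there is more than 80% chance" that the rate is above 30%.

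The same section sets a run-in: "The evaluation of the toxicity data will begin after enrollment of 8 patients". The boundary list opens at 4/8 and 5/9. One exception covers the run-in: "for the first 8 patients, if 4 or more out of 4-7 patients experience toxicity, the trial will also be stopped".

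Other safeguards apply from the first patient. Section 4.2.3 states that "toxicity will be monitored closely in all patients". Section 4.9 states that "all SAEs, expected or unexpected, must be reported to the IRB, regardless of attribution", within 5 working days. Neither links a number of events to a pause in enrolment.

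On timing, 4.2.1 says: "A maximum of 22 patients will be enrolled in MDACC at an estimated accrual rate of 1 patient every 2 months". Section 4.2.3 gives no window within which a toxicity must occur to be counted. Under 4.5.3, laboratory follow-up runs to 6 months, and "Adverse events will be assessed on the same timetable".

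**The concern.** The plan ends the trial at 4 events in 8 patients. By its own posterior measure, 3 events in the first 3, 4 or 5 patients are stronger evidence of excess toxicity, but they fall in the run-in and miss the 4-event exception. As written, the next patient can be treated without a recorded decision.

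The treatment is major cytoreductive surgery with heated cisplatin, open to children from 1 year of age (2.1.1). Elevated creatinine was the dose-limiting toxicity in phase I (Background), and 4.4.1 reports renal insufficiency in two patients perfused twice at 100 mg/m². An early cluster of counted renal events is therefore a plausible case to plan for.

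**Working it through.** **Inputs.** From 4.2.3: the beta(0.6, 1.4) prior, the 30% rate limit, the 0.80 threshold, the boundary list, the 4-of-4-to-7 stop and Table 2. From 4.2.1: a maximum of 22 patients.

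**1. Reproduce the plan's own figures.** After x events in n patients the posterior is beta(0.6 + x, 1.4 + n − x), and the monitored quantity is its tail above 0.30. This gives 3/8 = 0.631 and 4/8 = 0.846, then 4/9 = 0.782 and 5/9 = 0.922. The printed boundaries at 8 and 9 are confirmed.

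For Table 2 I carried the binomial path forward exactly, with a maximum of 20. That maximum is an assumption: the upper percentiles in Table 1 are 20, while 4.2.1 says 22.

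| True rate | Table 2 | Posterior rule at patients 8–19, plus 4-of-4-to-7 | Posterior rule from patient 1 |
|---|---|---|---|
| 0.1 | 0.006 | 0.007 | 0.037 |
| 0.2 | 0.094 | 0.094 | 0.180 |
| 0.3 | 0.344 | 0.345 | 0.443 |
| 0.4 | 0.665 | 0.669 | 0.730 |
| 0.5 | 0.897 | 0.895 | 0.916 |

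Table 2 fits the run-in and does not fit looks from patient 1.

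**2. Posteriors inside the run-in.**

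| Events/patients | Tail above 0.30 | Against 0.846 (4/8) |
|---|---|---|
| 2/2 | 0.928 | above |
| 2/3 | 0.838 | below |
| 3/3 | 0.976 | above |
| 3/4 | 0.935 | above |
| 3/5 | 0.875 | above |
| 3/6 | 0.800 | below |
| 3/7 | 0.717 | below |

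With three events as the minimum, the 4/8 benchmark selects exactly 3/3, 3/4 and 3/5.

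**3. How often this happens.** Reaching 3 events by patient 5 is the same as 3 or more events among 5, so the probability is P(X ≥ 3), X ~ Bin(5, p). At p = 0.3: 10(0.027)(0.49) + 5(0.0081)(0.7) + 0.00243 = 0.163. For p = 0.1 to 0.5 the values are 0.009, 0.058, 0.163, 0.317 and 0.500.

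**4. What the existing rules already catch.** From 3 events at patient n, one more event by patient 8 stops the trial, with probability 1 − (1 − p)^(8 − n). The weights for n = 3, 4, 5 are p³, 3p³(1 − p) and 6p³(1 − p)². At p = 0.3: (0.0270 × 0.832 + 0.0567 × 0.760 + 0.0794 × 0.657)/0.163 = 0.72. At 0.4 and 0.5 the results are 0.84 and 0.92.

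**5. Further patients treated after the third event.** Assumptions: printed boundaries, 9 events at 19–21 patients (the list ends at 18), maximum 22. The means are 5.8, 3.8 and 2.5 at true rates of 30%, 40% and 50%. With no stop after patient 18 they are 5.9, 3.8 and 2.5; with boundaries recalculated from the posterior rule, 5.2, 3.3 and 2.3. All are upper figures, because they ignore the futility stop in 4.2.2 that runs alongside.

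**6. Price of a hold.** Under the same assumptions, the hold would pause a trial that the printed boundaries never stop in 0.6%, 2.4% and 3.4% of trials at 10%, 20% and 30%. Used instead as a hard stop, it would raise early stopping from 0.5% to 1.1%, from 7.1% to 9.5% and from 28.6% to 32.0%. At a 50% rate the mean number treated would fall from 10.4 to 9.2.

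**The case against.** A run-in exists so that posteriors from a handful of patients do not drive action. The prior carries the weight of two patients, so a single event in one patient already gives 0.789. Holding 3 to 5 patients to the 4/8 posterior could be said to ignore the reason for a run-in. The trigger is also a choice: 2/2 (0.928) is above the benchmark and is left out only because it rests on two patients. Close monitoring, IRB reporting and the 4-event stop already cover most of the ground, and the dose comes from the same centre's phase I trial. All of this stands. It argues for a review instead of an automatic stop, and for low priority. It does not supply the missing action for three early events.

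Three stronger readings are tempting and not supported.

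- A reader might infer that the run-in is a mistake, or that it makes Table 2 wrong. Table 2 reproduces with the run-in in place.
- A reader might infer that the any-time wording already stops the trial at 3/3. The run-in sentence, the 4-of-4-to-7 clause and Table 2 together show that it was not meant to operate that way before patient 8.
- A reader might infer that a hold saves 5.8 patients. That figure is for a 30% rate, which the rule itself does not treat as excessive, and it ignores futility stopping. A hold guarantees no saving, and even a hard stop saves only about 1.2 patients on average at 50% (10.4 − 9.2).

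**Conclusion.** The gap is real and narrow: 3/3, 3/4 and 3/5 exceed both the 0.80 threshold and the plan's own first tabulated stop, and the protocol attaches no action to them. It is an optional improvement to patient safety and leaves the validity of the design untouched. The posteriors need nothing beyond the stated prior. The frequencies also assume independent patients with a common toxicity rate, and the further-patient figures rest on the assumptions given with them.

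The practical value depends on when toxicity is known. With a 30-day window and one patient every 2 months, each count would be complete before the next patient. With a 3- or 6-month window, 1 to 3 more patients could be treated first.

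**What to change.** Keep the run-in, the 4-of-4-to-7 stop and the later boundaries, and add one sentence to 4.2.3:

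> If 3 of the first 3, 4 or 5 evaluated patients have a counted toxicity, enrolment is held until the investigator, the study biostatistician and the IRB have reviewed the cases and documented the decision to continue or stop.

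The hold acts on events known when the next patient is considered. As a review hold it alters no boundary, so Table 2 need not be restated on its account; as a hard stop, Table 2 would have to be recalculated.

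The cost is one sentence, with no new committee and no new data. The review step is new, and the documents do not show how long it would take. The hold fires in 0.9%, 5.8% and 16.3% of trials at true rates of 10%, 20% and 30%. At a 10% rate about 69% of those holds (0.0059/0.0086) would interrupt a trial that the printed boundaries never stop; at 20% it is about 42% (0.0244/0.0579).

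I would not reword the start of the posterior rule as part of this change. That would be clarification only, and it meets a separate matter: from patient 10 the list ("and 6 or more patients out of 10, 11 and 12 patients, 7 or more patients out of 13, 14 and 15 patients") is looser than the rule at several counts. For example, 5/10 gives 0.880 and is not a printed stop.
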